3.1.3 N8-GP Clinical Data

In accordance with the European Medicines Agency (EMA) Guidelines⁷, the clinical programme for N8-GP was initiated by a pharmacokinetic (PK) trial to document the essential PK characteristics of the product and to achieve initial safety information.

By April 2011, 26 PTPs were dosed with N8-GP in the NN7088-3776 (pathfinderTM 1) trial and had undergone a safety and PK investigation. The phase 1 trial has successfully been concluded with no safety concerns. No FVIII inhibitors were detected and no treatment related SAEs were reported. The half-life was pro-longed with approx 1.6-fold compared to the patients previous FVIII product. For further information on medicinal aspects, non-clinical data and quality of N8-GP, please refer to the Investigator's Brochure (IB)⁸.

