5.3.1 Prophylaxis

In the prophylaxis arm, one single bolus dose of 50 U/kg BW of N8-GP is administered intravenously every 4 days (96 hours interval). The dose chosen is based on phase 1 data from the pathfinderTM 1 trial and is chosen to ensure a trough level of >1% FVIII:C activity in the majority of patients in the prophylaxis arm. During treatment a shortening of the dosing interval for prophylaxis to twice weekly may be undertaken at the Investigator's discretion, if deemed necessary for the individual patient (see section [5.3.2](#)). If the dosing regimen is changed to twice weekly, doses should be separated with at least 3 calendar days and no more than 4 calendar days. Other changes

of the dose or dosing interval for prophylaxis are not allowed within the trial. However, extra doses of N8-GP will be administered if a patient experiences a treatment requiring bleeding episode or in case of minor surgery.

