5.3.2 Treatment of Bleeding episodes

A treatment requiring bleeding episode is in this trial defined as a bleed that require treatment with a coagulation factor product e.g. N8-GP. If a patient experiences a treatment requiring bleed it must be treated as soon as it is identified (~~refer to Section 8.2.1~~).

...

~~For the treatment of bleeding episodes, doses will be based on World Federation of Haemophilia (WFH) guidelines¹ (see Section 8.2.1). For treatment of a bleed, all on demand and prophylaxis patients will be treated with doses between 20-75 U/kg BW (the recommended standard dose will be 50 U/kg). to achieve a desired dose level based on the severity and location of the bleeding episode. Each unit of N8-GP will raise the FVIII level with approximately 2%. For recommended dose levels see table 1. Further guidance on the treatment of bleeds may be found in WFH guideline¹.~~

The dosage is calculated by multiplying the patient's weight in kilograms by the factor level desired multiplied by 0.5. This will indicate the number of N8-GP units required.

Example: 50 kg x 40 (% level desired) x 0.5 = 1 000 units of N8-GP.

Table 2–1 Guide for dosing in bleeding episodes

Type of haemorrhage	Desired level	Recommended dose
Joint, muscle (except iliopsoas)	40% - 60%	20 - 30 U per kg
CNS/head, Throat and neck, Gastrointestinal, Iliopsoas	80% - 100%	40 – 50 U per kg

Based on recommendations WFH guidelines.

The effect of initial N8-GP dose on the clinical symptoms should be closely monitored and the need for a second dose should be evaluated within 8 hours after the initial N8-GP dose. If further doses are considered necessary to treat the bleeding episode, the patient is recommended to contact the investigator.

The maximum dose to be administered to a patient within 24 hours (hrs) is 200 U/kg BW. The dose is recommended to be divided and only considered under exceptional circumstance such as serious trauma or severe bleeding episodes.

Age and body weight are markedly correlated in children and adolescents. As the dosing of N8-GP takes body weight into account no further adjustment is needed in the adolescents included in this trial.

Due to individual patient's bleeding pattern during the trial, an adaptation in dosing regimen to 50 U/kg twice weekly will be permitted at the investigator's discretion. If the dosing regimen is changed to twice weekly, doses should be separated by at least 3 calendar days and no more than 4 calendar days.

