The pre-dose FVIII activity levels assessed from after at least 4 PPX dosing intervals will be analysed to get an estimate of the pre-dose level for N8-GP at steady state. The model will be a mixed model on the logarithmic plasma activity levels with dose and age as a factor and patient as a random effect. Plasma concentrations below lower limit of quantification (LLOQ) will be set to half the value of the LLOQ. The estimated pre-dose FVIII level will be presented together with the 95% confidence intervals. Trial duration for the main phase differs between patients, but all patients reach at least Visit 8 prior to being transferred to Visit 13 (end of main phase). Therefore, the analysis will be performed both on pre-dose values from main and extension phase part 1 and furthermore including only pre-dose values up to visit 8.

A sensitivity analysis including all data after at least 4 PPX dosing intervals will also be performed for both cases.

Furthermore the same analyses will be performed for measurements from the randomised patients in the extension phase part 1.

Pre-dose activity, post-dose activity and incremental recovery will be summarised by visit. Furthermore, mean pre-dose activity and mean post-dose activity will be plotted vs. time.

In extension phase part 2, the only PK endpoint that will be summarised by visit is incremental recovery for all prophylaxis patients, since incremental recovery is independent of dose and dosing frequency. Incremental recovery will be calculated using the same activity measurements as used for estimation of recovery and trough levels.

In extension phase part 2 the following rules have been added to the rules for activity measurements listed above (the new rules are also applied to activity measurements from main and extension phase part 1)

- Samples from visits when changing treatment regimen (e.g. from every 4 day dosing to every 7 day dosing) will be excluded (this rule replaces the rule for randomised patients changing from every 7 day dosing to every 4 day dosing)
- Samples taken at “return visit” from the PK-trial (NN7088-4033) are excluded.
- If the FVIII activity is above 3.0 IU/ml based on one of the three clot assays and the ratio of Clot PSS (chrom)/Chrom PSS > 1.5, all clot data for this sample time point will be excluded. The reason for this rule is that plasma samples can be activated during pre-

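### Setting pre-dose FVIII values below the LLOQ to half the LLOQ can bias the every-7-day trough estimate upward with poor interval coverage, and no planned analysis tests the rule

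*SAP*

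**What the plan says.** Under Steady state PK, SAP 2.2.4.1 estimates the pre-dose FVIII level with a "mixed model on the logarithmic plasma activity levels with dose and age as a factor and patient as a random effect" and reports it with a 95% confidence interval. For low values the rule is: "Plasma concentrations below lower limit of quantification (LLOQ) will be set to half the value of the LLOQ". It then adds: "Furthermore the same analyses will be performed for measurements from the randomised patients in the extension phase part 1". Those patients are on 50 U/kg every 4 days or 75 U/kg every 7 days (Protocol 5.3.1 as amended).

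One sensitivity analysis is attached to this model: "A sensitivity analysis including all data after at least 4 PPX dosing intervals will also be performed for both cases". It restores samples removed by the exclusion rules and leaves the treatment of low values unchanged. The LLOQ is not stated, and no count of values below it is planned.

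**The concern.** Replacing a few low values by one constant does little harm. When a large share is replaced, the geometric mean is pulled towards that constant. The replaced values also lose their spread, so the interval tends to be too narrow. Levels 168 h after a dose are the ones most likely to be affected.

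The documents point the same way. Protocol 5.3.3 and 6.4 use 7 days without N8-GP as the wash-out before the second PK session, and 8.3.2.1 falls back on 7 days when 96 h does not prevent assay interference. SAP 2.8 plans for time spent below 1%. This is only suggestive, because the SAP questions a wash-out only when pre-dose activity exceeds 5%.

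At stake is the trough estimate for the regimen that extension part 1 was set up to study. Trough level is a listed supportive endpoint.

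**Working it through.** **Inputs from the documents**
- Regimens: 50 U/kg every 96 h and 75 U/kg every 168 h.
- Recovery: "Each unit of N8-GP will raise the FVIII level with approximately 2" per cent (Protocol 5.3.2, Amendment 2). This is a dosing guide, not a reported PK result.
- Half-life, as a ratio only: "The half-life was pro-longed with approx 1.6-fold compared to the patients previous FVIII product" (Protocol 3.1.3).
- Kinetic form: linear, one compartment (SAP 2.8).

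**Assumed inputs**
- Previous-product half-life 10 to 14 h, so N8-GP 16 to 22.4 h (multiplying by 1.6).
- LLOQ 0.5, 1 or 2%, with 0.3% as an extra case.

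**Agreement with the plan's own figures.** The dosing example reproduces: 50 × 40 × 0.5 = 1000 U. The 50 U/kg dose "is chosen to ensure a trough level of >1% FVIII:C activity in the majority of patients in the prophylaxis arm". From a peak of 50 × 2% = 100%, a level of 1% at 96 h needs a half-life of 96 / log2(100) = 14.4 h, or 14.4 / 1.6 = 9.0 h for the previous product. The assumed range is compatible with this target.

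**Typical steady-state trough.** Trough = dose × 2% × 2^(−τ/T) / (1 − 2^(−τ/T)). At T = 19.2 h:
- Every 4 days: 100% × 2^(−5) / (1 − 2^(−5)) = 3.23%.
- Every 7 days: 150% × 2^(−8.75) / (1 − 2^(−8.75)) = 0.35%.

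At 16 h and 22.4 h the every-7-day value is 0.10% and 0.83%. It reaches the LLOQ only when the half-life is at least 18.7 h (LLOQ 0.3%), 20.4 h (0.5%), 23.2 h (1%) or 27.0 h (2%).

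**Effect of the rule, first simulation.** Assumptions: 30 every-7-day patients with 5 samples each, between-patient CV of about 25% for half-life and 15% for recovery, and 20% residual error. Values below the LLOQ were set to half of it, and a t-interval was taken on patient mean logs (1000 replicates). The true geometric mean lies a little below the typical-patient value because half-life varies between patients.

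| Half-life | True | Estimate at LLOQ 0.5 / 1 / 2% | 95% CI coverage |
|---|---|---|---|
| 16 h | 0.08% | 0.32 / 0.55 / 1.02% | 0 / 0 / 0% |
| 19.2 h | 0.29% | 0.48 / 0.68 / 1.12% | 6 / 0 / 0% |
| 22.4 h | 0.71% | 0.83 / 0.99 / 1.36% | 92 / 47 / 0% |

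Repeat runs differ by a few points. The share below the LLOQ runs from about 36% (22.4 h, LLOQ 0.5%) to 98% (16 h, LLOQ 2%); at 19.2 h it is 60 / 77 / 91%. At 22.4 h with LLOQ 0.3%, coverage is about 94%. Every-4-day estimates at 19.2 h are 2.9 to 3.0% against a true 2.9%.

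**Effect of the rule, second simulation.** This used a random-intercept model pooling both regimens: 30 and 15 patients, 4 samples each, half-life CV 20%, residual SD 0.3 on the log scale, 30 runs per setting, age omitted.

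| Previous-product half-life, LLOQ | Below LLOQ | No censoring (95% CI) | Half-LLOQ rule (95% CI) |
|---|---|---|---|
| 10 h, 1% | 96% | 0.10% (0.06–0.15) | 0.52% (0.44–0.62) |
| 12 h, 1% | 82% | 0.30% (0.20–0.46) | 0.62% (0.50–0.76) |
| 14 h, 1% | 59% | 0.73% (0.51–1.04) | 0.89% (0.68–1.16) |
| 14 h, 0.5% | 33% | 0.75% (0.52–1.07) | 0.80% (0.58–1.09) |

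In the first row, the interval from every-7-day patients alone would be 0.49 to 0.55, so pooling the variance weakens the narrowing. With this half-life CV, the every-4-day share below an LLOQ of 1% is 31% at a previous-product half-life of 10 h, 8% at 12 h and 2% at 14 h.

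**Left-censored likelihood on the first simulation's data** (40 runs per setting). At 19.2 h with LLOQ 0.5% or 1%, the estimate was 0.38 to 0.39% with 85% coverage. At 22.4 h coverage was 90 to 100%. Some upward bias remains under heavy censoring. A 15-point quadrature failed and a fine grid was needed.

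**The case against.** The strongest objection is that the two deciding inputs are assumed. A reader might infer that the protocol's own PK figures put most every-7-day troughs below the limit. They do not: the protocol gives a half-life ratio and a dosing-guide recovery, and neither document gives an LLOQ. At LLOQ 0.5% and 22.4 h, coverage is about 90%. This objection stands, and the point is conditional on the assay and the half-life.

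Three other inferences are tempting and not supported:
- *That the LLOQ decides whether the estimate lies above or below 1%.* In the first table, all six estimates at LLOQ 0.5% or 1% are below 1%, as are the true values. The side changes only at LLOQ 2%, where half the LLOQ is itself 1%. The 1% rationale in Protocol 5.3.1 also concerns 50 U/kg every 4 days in the main phase; no trough target is set for every 7 days.
- *That a planned comparison between regimens is biased.* The SAP plans an estimated level with an interval, not a ratio or difference between regimens.
- *That the every-7-day efficacy conclusion is affected.* It rests on the upper 95% limit for ABR being below 8.5 (SAP 2.10).

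The simulations also simplify. They omit the ±2-day sampling window; at 19.2 h the level is 1.97% at 120 h and 0.06% at 216 h. They ignore endogenous FVIII. They ignore selection too: only patients with 0 to 2 bleeds in 6 months were eligible, and samples after a switch back are excluded. Selection could raise the observed troughs, though the documents do not establish this.

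Timing limits the reach. The part 1 interim has been reported, and for part 2 the SAP summarises only incremental recovery by visit. However, its new exclusion rules also apply to main-phase and part 1 measurements. Trough values are listed, so individual values can be inspected, but listings do not repair the model estimate.

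**Conclusion.** The point holds in conditional form. The substitution rule reaches the every-7-day patients, and nothing in the plan tests it. Over assumed half-lives of 16 to 22 h and LLOQs of 0.5 to 2%, the every-7-day estimate is biased upward, by a factor of about 1.7 to 3.9 at 19.2 h (0.48 / 0.29 and 1.12 / 0.29). Coverage is near zero in seven of the nine settings, 47% in one and about 90% in one. The effect is small when the LLOQ is 0.3 to 0.5% and the half-life is 22 h or more. The every-4-day estimate is little affected, except at the shortest half-life or highest LLOQ. This is a supportive PK estimate outside the confirmatory tests.

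**What to change.** In SAP 2.2.4.1, Steady state PK:
1. State the LLOQ of each assay used for the pre-dose model.
2. Report by regimen the number and percentage of pre-dose samples below the LLOQ and below 1%.
3. For the randomised regimens, estimate the pre-dose level with a left-censored likelihood in the same log-scale mixed model (dose, age, patient as random effect). Values below the LLOQ contribute the probability of lying below it. Specify enough quadrature points and check that the result is stable as they increase.
4. Keep half-LLOQ substitution as a sensitivity analysis.

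This needs no new data. The cost is some SAP wording and one further model fit, for instance in PROC NLMIXED. As the part 1 interim has been reported, it would be a supplementary re-analysis of those data. The every-7-day estimate will probably be lower with a wider interval, and some bias will remain if most values are censored. Item 2 lets the reader judge that.

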2.3 Safety Endpoints

Adverse Events (AEs) and Serious Adverse Events (SAEs) reported during the trial

Treatment emergent AEs (TEAEs defined as AEs occurring after dosing with trial product) and treatment emergent SAEs (TESAEs) will be summarised by frequency of events and frequency of patients with any event. Similar summaries cross-classified by severity and by causal relation to trial product will be made.

Furthermore, listings will be provided displaying all TEAEs and TESAEs including pertinent clinical information.

Changes in vital signs (blood pressures, pulse, temperature, respiratory rate)

These endpoints will be presented and listed

Other safety parameters

All additional safety parameters such as laboratory parameters, vital signs and physical examinations will be presented and listed.

2.4 Exploratory endpoints

Incidence of anti-N8-GP antibodies (non-neutralising)

Anti-N8-GP antibodies (non-neutralising) will be listed.

Anti-CHO HCP antibodies

Number of samples with negative/positive will be summarised by visit.

Anti-PEG antibodies

Plots will be created of incremental recovery according to PEG antibody status at baseline and during the trial.

2.5 Interim Analysis

All data from the Main Phase of the trial will be analysed and reported when all patients have reached at least 50 EDs (except for patients having had surgery as part of pathfinder™3), and all patients have had their first visit after 50 EDs where all planned assessments including inhibitors have been performed. The analysis of the main phase of the trial will be based on all data up to the patient's last visit at this point. All main conclusions from the trial will be based on this reporting.

Furthermore, an interim analysis was performed when all patients had completed extension phase part 1. The interim for the extension phase part 2 will cover all data from the main phase and extension phase 1+2 up to last visit before 15-Aug-2017.

2.6 Sequential Safety Analysis/Safety Monitoring

Not applicable (NA).

2.7 Explorative Statistical Analysis for Pharmacogenetics and Biomarkers

NA.

2.8 PK and/or PD Modelling

The relationship between plasma concentration and bleeding frequency will be investigated. Based on each individuals PK assessments (full PK from some patients but only recovery and troughs for most patients) the time to 5%, 3% and 1% FVIII activity after each dose given will be calculated and the bleeding rates for each period (>5%, 3-5%, 1-3% and <1%) will be calculated and listed and summarised.

A statistical comparison will be made between the bleeding rates above and below 1% FVIII activity. This will be done based on a Poisson regression with patient above or below 1% activity as fixed effects. The model will allow for over-dispersion (estimated using Pearsons chi-square divided by the degrees of freedom) and will use log duration (above 1% activity and below 1% activity respectively) as offset. For computational reasons only patients with at least one bleeding episode will be included and similarly only patients with at least 2 weeks cumulative time under 1% activity and 2 weeks cumulative time over 1% activity will be included.

The following PK parameters will be estimated using a one-compartment population PK model:

- CL_{70kg} (L/h) Population median clearance in a patient of weight 70 kg
 - V_{70kg} (L) Population median volume of distribution in a patient of weight 70 kg
 - $\beta_{CL,BW}$ Allometric exponent for relation between median CL and BW
 - $\beta_{V,BW}$ Allometric exponent for relation between median V and BW
- Extrapolated population PK parameters:
- $C_{max,SS}$ Predicted maximal plasma level of FVIII activity in steady state
 - $AUC\tau$ Predicted total exposure to FVIII activity during a single dosing interval in steady state

PK and possible PK/PD modelling are considered exploratory analyses that may not be reported in the clinical trial report. The PK assay results to be used for modelling are chromogenic FVIII activities measured against N8-GP reference material.

Population PK modelling will be done as a combined analysis with data from the first human dose trial pathfinder™ 1 with the main scope of assessing the influence of demographic covariates such as BW and possibly race on PK properties of N8-GP. The population PK model of which maximum-likelihood parameter values are to be estimated is a linear one-compartment model parameterised with clearance CL and volume of distribution V.

The final output of the PK modelling is predictions of FVIII activity exposure parameters (C_{max} and $AUC\tau$) at steady state in proposed prophylaxis dosing regimes for patients of BW 10 kg, 25 kg, 50 kg, 70 kg and 100 kg and of any race sufficiently well represented in the trial to allow for assessment (min. 20 PK samples from min. 5 different patients).

2.9 Health Economics and/or Patient Reported Outcome

PROs will in the Main Phase be assessed through PRO questionnaires at screening visit (Visit 1) and end of trial visit for patients in the on-demand arm and for patients in the prophylaxis arm.

The main PRO endpoint will be subgroup total scores. Changes in scores over time of the main PRO endpoints at Visit 1 to end of main visit will be explored and presented graphically.

Evaluations of PRO data will alone be based on descriptive statistics, i.e. summary tables, listings and figures.

HE calculations will be performed separately by the Novo Nordisk HE department. Novo Nordisk A/S will be responsible for the statistical analysis.

2.10 Analyses of Extension Phase Data

Data from part 1 of the Extension Phase

The main objective of part 1 of the Extension Phase is to investigate the safety and efficacy of every 7 day dosing by evaluating ABR for this dosing regimen and comparing it to the same historical bleeding episode rates as used in the primary analysis for the co-primary efficacy endpoint in the Main Phase. Prophylactic effect of every 7 day dosing will be concluded if the bleeding rate is significantly below 50% of the historical on-demand bleeding rate (i.e. significantly lower than 12) as well as within 25% of the historical prophylaxis bleeding rates (i.e. significantly lower than $6.8 \times 1.25 = 8.5$). Since both must be met in practice it must be shown that the bleeding rate is significantly lower than 8.5.

An analysis similar to that for the co-primary endpoint in the Main Phase will be carried out for the bleeding episodes in the two randomised treatment regimens during the Extension Phase part 1, adding treatment regimen as a factor to the model. Subjects switching from the every 7 day dosing arm to the non-randomised every 4 day dosing arm will be handled as withdrawals in this analysis.

The imputation for withdrawals will be similar to that for the Main Phase, except that planned maximum duration is now 6 months.

Estimates of the annualised bleeding rates for each randomised regimen will be provided with 95% confidence intervals. Prophylactic effect of every 7 day dosing will be concluded if the upper limit of the 95% confidence intervals (CI) is below 8.5. In addition, the two randomised treatment regimens will be compared by reporting the estimated ratio between the two randomised treatment regimens with corresponding 95% confidence interval.

As for the co-primary endpoint in the Main Phase, a sensitivity analysis will be carried out where bleeding episodes for withdrawals are not imputed.

ABR based on accumulated number of bleeding episodes (Main Phase + Extension Phase part 1) will be evaluated for the every 4 day dosing regimens combined, i.e., combining the randomised and non-randomised arm. The model used will be the same as for the primary analysis of the Main Phase data.

Only treatment requiring bleeding episodes will be considered in the above evaluations of ABR. Incidence rate of FVIII-inhibitor and haemostatic effect of N8-GP when used for treatment of bleeding episodes will be evaluated based on accumulated data (Main Phase + Extension Phase part 1).

Adverse events, consumption of N8-GP, recovery and pre-dose levels will be summarised based on accumulated data (Main + Extension Phase part 1) by treatment regimen combining the every 4 day dosing regimens. In addition, separate summaries including data from part 1 only will be presented by treatment regimen for the randomised subset of patients to support the main objective of part 1 of the Extension Phase.

Other safety endpoints will be summarised based on accumulated data (Main Phase + Extension Phase part 1). Binding non-inhibitory antibodies will be listed.

PRO endpoints at end the Extension Phase part 1 will be evaluated and presented as described in section 18.9.

Data from part 2 of the Extension Phase

The main objective of extension phase part 2 is to collect long term safety and efficacy data.

ABR will be calculated as for the co-primary endpoint in the main phase, but based on the accumulated data, i.e. combined data from main phase, extension phase part 1 and extension phase part 2. Furthermore, sensitivity analyses are performed based on actual bleeding episodes and exposure times (i.e. without imputation for withdrawn patients).

Incidence rate of FVIII-inhibitor and haemostatic effect of N8-GP when used for treatment of bleeding episodes will be evaluated based on accumulated data.

Adverse events and consumption of N8-GP will be summarised based on accumulated data by treatment regimen.

Incremental recovery will be summarised by visit for extension phase part 2 and furthermore be presented graphically in the following ways:

- By N8-GP production process (extension phase part 2 data)
- According to Anti-PEG-antibody status (accumulated data)

For Anti-CHO HCP-antibodies, the number of negative/positive samples will be summarised by visit.

Other safety endpoints will be listed and/or plotted based on accumulated data.

-

PRO endpoints for extension phase part 2 will be summarised by time since first dose (since timing of visits depend on treatment regimen). Time grouping will span a year, i.e. grouping being “1 - <2 years”, “2 - <3 years”,.... The two prophylaxis regimens will be considered as a combined prophylaxis treatment regimen.

